## **Power Considerations**

Contrast between vaccine and placebo groups: The study has at least 80% power (one-sided Fisher's exact test, with  $\alpha$ =0.05) to detect a

difference of 50%, 53% and 56% or more in the rate of positive responses between an active group ( $n_1$ =28) and the placebo group ( $n_2$ =7), assuming the rate of positive responses in the placebo group to be 1%, 5% and 10%, respectively.

Contrast between two active vaccine groups: The minimum detectable difference between the two vaccine groups is 28%, with  $\alpha$ =0.05 and 80% power (two-sided Fisher's exact test), based on an assumption of 1% positive response rate in one of the two groups. If the response rate in one group was 10% and 20%, the minimum detectable difference would be 35% and 39%, respectively (i.e., the corresponding response rates in the other group would have to be 45% and 59%).

The criterion to be used for the demonstration of non-inferiority of the immune response induced by  $F4co/AS01_E$  compared to  $F4co/AS01_B$  is the following:

The upper limit of the 95 % CI for the ratio of the magnitude of the CD4+ CD40L+ T cells expressing at least IL-2, between both groups, at 2 weeks post second vaccination, is below 1.5.

Power considerations for the comparison of  $AS01_E$  to  $AS01_B$  are based on the values observed for the number of CD4+ T cells expressing at least IL-2 in GSK study PRO-HIV-005. A sample size of 27 subjects per group will provide a power of 80% to either exclude a difference higher than 1.5 fold between both adjuvants, assuming the same intensity for the CD4 T cell expressing at least IL-2 (with a one-sided alpha level of 0.025 and assuming a standard deviation of 0.223 for the log10 intensity).

### Planned Statistical Analyses

At 1 month after the end of the vaccination regimen and at the end of the study, an analysis will be prepared according to a pre-specified statistical analysis plan.

Based on the previous experience with IAVI Phase I/II Investigational Product studies, it is expected that the amount of missing, unused or spurious data will be insignificant. Unused and spurious data will be listed separately and excluded from the statistical analysis. Missing data will be excluded from the statistical analysis.

# 15.0 QUALITY CONTROL AND QUALITY ASSURANCE

To ensure the quality and reliability of the data gathered and the ethical conduct of this study, a SOM has been developed.

Regular monitoring will be performed according to ICH-GCP as indicated in Section 17.3.

An independent audit of the study may be performed, if appropriate at the discretion of the Sponsor.

By signing the protocol, the Principal Investigators, agree to facilitate study related monitoring, audits, IRB/IEC review and regulatory inspection(s) and direct access to source documents. Such information will be treated as strictly confidential and under no circumstances will be made publicly available.

## 16.0 DATA AND BIOLOGICAL MATERIAL

All data and biological material collected through the study shall be managed in accordance with the Clinical Trial Agreement. Distribution and use of those data will be conducted by agreement of both parties, with the understanding that the data will be published (Section19 Publication).

The computerized raw data generated will be held by the DCC on behalf of the sponsor. The study site will also hold the final data files and tables generated for the purpose of analysis. Principal investigators or designees will have access to the clinical study database with appropriate blinding.

## 17.0 ADMINISTRATIVE STRUCTURE

The Principal Investigator will be responsible for all aspects of the study at the CRC.

## 17.1 Protocol Safety Review Team (PSRT)

A PSRT will be formed to monitor the clinical safety data. During the vaccination phase of the trial, the PSRT will review the clinical safety data on a weekly basis via electronic distribution of reports. An ad hoc PSRT review meeting will occur if any of the members of the PSRT requests a special review to discuss a specific safety issue or as specified in the Study Operations Manual.

The PSRT will consist of the IAVI Medical Monitor (PSRT chair), IAVI Medical Safety Monitor and Principal Investigators or a medically qualified delegate of the Principal Investigator. The IAVI CMO and GSK medical experts are ex officio members.

## 17.2 Safety Review Board (SRB)

The Safety Review Board (SRB) will oversee the safety monitoring of the study. The SRB will consist of independent clinicians/scientists/statisticians who are not involved in the study. Investigators responsible for the clinical care of volunteers or representative of the sponsor may not be a member of the SRB.

However, the SRB may invite the Principal Investigator or designee, sponsor and GSK representatives to an open session of the meeting to provide information on study conduct, available data or to respond to questions.

The SRB will review the blinded study data for the first 28 volunteers in groups A/B, for the first 14 volunteers in groups C and for the first 14 volunteers in group

D at 2 weeks post month 1, and 2 weeks post month 4 vaccinations. Interim reviews may be specifically requested (see Section 17.1.2).

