## **STATISTICAL CONSIDERATIONS:** Collected data will be identified only by a volunteer identification number. Safety data will be reviewed by an independent Safety Review Board (SRB) for the first 28 volunteers in groups A/B, the first 14 volunteers in group C and the first 14 volunteers in group D at 2 weeks post month 1 and 2 weeks post month 4. Ad-hoc review may be specifically requested by the sponsor, GSK, the Principal Investigators or by the SRB.

At 1 month after the end of the vaccination regimen and at the end of the study, an analysis will be performed according to a pre-specified statistical analysis plan. The proportion of volunteers in each group who become HIV-infected will be analyzed (if any infections occur). Safety and tolerability will be addressed by examining the overall rates of adverse events and serious adverse events that might be associated with vaccination and the number of volunteers who experience these events. All clinical and routine laboratory data will be included in the safety analysis. Immunogenicity analyses will be performed in all volunteers who have received vaccine. Immune responses may be compared to results in the earlier IAVI-sponsored studies and earlier GSK studies.

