## 5.2.1 Duration of the Study

Volunteers will be screened up to 42 days before vaccination (up to 90 days for Ad35 neutralizing antibody) and will be followed for 12 months after the last vaccination (16 months total participation).

It is estimated that it will take approximately 5 months to complete enrolment.

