## 5.2.2 Study Population

The study population consists of healthy male or female adults aged 18 to 40 years who are willing to undergo HIV testing, use an effective method of contraception, and who in the opinion of the investigator or designee, understand the study and provide written informed consent.

Approximately 140 volunteers (112 vaccine /28 placebo recipients) will be included in the study. An over-enrolment of up to 7% (approximately 10 additional volunteers) will be permitted in the study to facilitate rapid enrolment.

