## 13.3 Data Entry at the Clinical Research Centre

The data collected at the CRC will be entered onto the CRFs by the study staff. To provide for real time assessment of safety, data should be entered as soon as reasonably feasible (e.g., within one week) after a visit. Immunogenicity results will be transferred within 2 weeks after the assay is performed.

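### The two scheduled Safety Review Board reviews are limited to the first 56 of 140 volunteers; cumulative data on all vaccinated volunteers could be supplied at little cost

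*Protocol*

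**What the plan says.** Section 17.2 of the protocol reads "The SRB will review the blinded study data for the first 28 volunteers in groups A/B, for the first 14 volunteers in groups C", then adds the first 14 volunteers of group "D at 2 weeks post month 1, and 2 weeks post month 4 vaccinations". The synopsis, under Statistical Considerations, sets the same limit: "for the first 28 volunteers in groups A/B, the first 14 volunteers in group C and the first 14 volunteers in group D". Section 17.2.1 lists the kinds of event the board is shown (related clinical events, confirmed related laboratory events, all SAEs) but does not say whose events beyond that cohort.

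On size and pace, section 5.2.2 has "Approximately 140 volunteers (112 vaccine /28 placebo recipients) will be included in the study" and also "An over-enrolment of up to 7% (approximately 10 additional volunteers) will be permitted in the study to facilitate rapid enrolment". Section 5.2.1 has "It is estimated that it will take approximately 5 months to complete enrolment". Section 13.3 has "To provide for real time assessment of safety, data should be entered as soon as reasonably feasible (e.g., within one week) after a visit".

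Other safety channels apply to all volunteers:
- weekly PSRT review during the vaccination phase (17.1);
- notification of product-related SAEs to the board (10.4);
- event-triggered pausing with board review, and ad hoc review on request (17.3);
- interim and final reports shared with the board as appropriate (13.4), and progress reports (17.4).

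**The concern.** The first 28/14/14 volunteers do two jobs in this text. They set when each review happens, and they limit whose data the board sees. Only the first job is needed. The second means that the board can meet while later volunteers' data are already in the database, and its scheduled package leaves those data out.

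The data at issue are those below the pausing threshold. The criteria in section 17.3 are related SAEs or deaths, injection-site ulceration, sterile abscess or necrosis, and severe allergic reactions. A cluster of severe but non-serious systemic reactions, or of laboratory abnormalities, meets none of them. Section 3.1.2 shows that such a pattern can occur. In the earlier dose-escalation trial of Ad35-GRIN/ENV, 5 of 14 volunteers in the highest dose group, a level not used here, had severe transient systemic reactions, and no SAE was reported. Group D receives both products together three times. In later volunteers a pattern of this kind would be seen weekly by the PSRT. That team consists of sponsor monitors and investigators, and section 17.2 bars sponsor representatives and treating investigators from the board.

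**Working it through.** **The protocol's own precision figure.** Section 14.2.1 gives zero-event upper bounds (two-sided 95%, Clopper-Pearson) of 0.03 for n=112 and 0.12 for n=28. The formula is 1 − 0.025^(1/n).
- n=112: 0.0324.
- n=28: 0.1234.

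Both reproduce.

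**Coverage.**
- Covered: 28 + 14 + 14 = 56, and 56/140 = 40%.
- Not covered: 140 − 56 = 84 (60%). With full over-enrolment to 150, 94/150 = 63%.
- At 4:1 allocation, about 56 × 0.8 = 45 vaccinees are expected among the 56. The zero-event bound for 45 is 0.079.

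**Data that exist at each review.** Assumptions:
- The 140 enrol over 5 × 30.4375 = 152 days, with all groups filling at the same rate.
- Enrolment is not held for the reviews.
- The reviews fall 42 and 126 days after the 56th enrolment. These are the visit days two weeks after the month 1 and month 4 vaccinations in Appendices A and C. Group C has no month 1 vaccination and no week 6 visit, so for that group day 42 is only a calendar point.

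Under uniform accrual the 56th volunteer enrols at 0.4 × 152 = day 61. The reviews then fall at about day 103 and day 187. The ranges come from a front-loaded curve (enrolment proportional to the square root of time) and a back-loaded curve (proportional to time squared).

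| Of the 84 later volunteers | Uniform | Front-loaded | Back-loaded |
|---|---|---|---|
| Review 1: enrolled | 39 | 36 | 60 |
| Review 1: at least 14 days of data | 26 | 26 | 37 |
| Review 2: enrolled | 84 | 83 | 84 |
| Review 2: at least 14 days of data | 84 | 77 | 84 |
| Review 2: reached day 42 | 77 | 62 | 84 |
| Review 2: reached day 126 | 0 | 0 | 0 |

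The last row is zero by construction, because the second review is timed from the 56th volunteer's day 126.

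**Group D, uniform accrual at 7 per month.**
- Scheduled cohort: 14 × 0.8 = about 11 vaccinees expected. Zero-event bound 1 − 0.025^(1/11) = 0.285.
- Past day 42 at the second review: 35 × (187 − 42)/152 = about 33, or about 26 vaccinees. The later volunteers contribute (33 − 14) × 0.8 = about 15 of them.
- For events through day 42 only, where all 26 have equal follow-up, the bound is 1 − 0.025^(1/26) = 0.132, against 0.285.
- Third dose (day 112): this needs enrolment by day 187 − 112 = 75, which is 35 × 75/152 = about 17 volunteers. Only the first 14 are two weeks past it.

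**Can the second review still inform dosing?** Across the trial, 140 × (1 − 75/152) = about 71 volunteers have not yet reached their month 4 vaccination at day 187.

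**The case against.** The strongest reply is that this is a coherent Phase I arrangement: independent review of an early cohort, followed by weekly PSRT review and sensitive pausing rules. One probably or definitely related SAE in any volunteer stops enrolment and vaccination, and a board review must be held within 2 business days. The board can also call its own ad hoc review. That stands, and it limits the size of the point.

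A reader might infer that the 84 have no board oversight, or that independent oversight of group D depends wholly on its first 11 or so vaccinees. The documents do not support either reading. The pausing rules, related-SAE notices and ad hoc reviews cover every volunteer, and the board also receives interim and progress reports. However, ad hoc review needs a prompt, and those reports carry no scheduled safety review of the later volunteers.

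It can also be said that section 17.2.1, with its references to all related events and all SAEs, widens the cohort. It defines content, not people, and section 17.2 and the synopsis both name the cohort. If a trigger alone was meant, the same one-sentence change makes that clear.

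Two further points stand. The protocol is silent on whether enrolment continues through the reviews; the 5-month estimate makes it likely but does not state it. And cumulative data would add little on the third dose. It would therefore be wrong to credit the change with better detection of third-dose events, or to compare detection chances between groups with unequal follow-up.

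**Conclusion.** The point holds as a cheap improvement to the plan, not as an absence of safety oversight. The counts are exact: 56 of 140 volunteers fall within the scheduled reviews and 84 do not, and the two places in the protocol agree. What the board is not scheduled to see is those 84 volunteers' non-serious reactogenicity and laboratory events below the pausing threshold.

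The amount of data left out depends on the assumed accrual. At the first review it is partial: 36 to 60 of the 84 are enrolled. At the second it is substantial: 62 to 84 have reached day 42, though none has reached two weeks after the month 4 vaccination. In group D the gain is about 15 vaccinees through two doses. The vaccinee counts are expectations at 4:1, since the board sees blinded data. The protocol gives no reason for leaving out data already collected.

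**What to change.** In section 17.2 and in the synopsis, keep the first 28 (A/B), 14 (C) and 14 (D) volunteers only as the trigger for the two reviews. Add one sentence: at each review the board receives cumulative safety data, by group, on every volunteer vaccinated by the data cut-off. Groups A and B can stay combined, as in the present wording, so the adjuvant blind is unaffected.

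This needs one amendment sentence in two places. It adds no visit, meeting or data collection, because section 13.3 already asks for entry within about a week of each visit. The downside is slightly larger tables and incomplete follow-up for later volunteers, so the tables should show how many have reached each vaccination. The change does not provide a scheduled review of the later volunteers after their month 4 vaccination.

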## **17.2.1 Content of Interim Review**

The SRB will be asked to review the following data:

- All clinical adverse events/reactogenicity judged by the Principal Investigator or designee to be possibly, probably or definitely related to the Investigational Product
- All laboratory adverse events confirmed on retest and judged by the Principal Investigator or designee to be possibly, probably, or definitely related to Investigational Product
- All Serious Adverse Events, independent of relationship to the Investigational Product.

## 17.3 Criteria for Pausing the Study

Enrollments and vaccinations will be stopped, and a safety review conducted by the SRB for any of the following criteria:

- one subject experiences a serious adverse event which is probably or definitely related to the investigational vaccine(s), or two or more subjects experience similar serious adverse events which are possibly related to the investigational vaccine(s);
- there is a subject death assessed as possibly, probably or definitely related to the investigational vaccine(s);
- one subject with injection site ulceration, sterile abscess or necrosis associated with vaccine administration occurs; or
- one subject with severe allergic reaction such as laryngospasm, bronchospasm or anaphylaxis associated with vaccine administration occurs.

The sponsor will request a review by the SRB, or the SRB chair if other SRB members cannot be convened, to be held within 2 business days of the sponsor learning of the event(s). Ad-hoc review may be specifically requested by the sponsor, GSK, the Principal Investigators or by the SRB. The study may be unblinded at the discretion of the SRB.

Following this review, the SRB will make a recommendation to the Sponsor, regarding the suspension or continuation of the vaccinations/ study. The Sponsor will inform GSK and the Principal Investigators without delay.

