### **10.4** Serious Adverse Events

An adverse event is reported as a "Serious Adverse Event" if it meets any the following criteria (as per ICH GCP Guidelines):

- Results in death
- Is life threatening

- Results in persistent or significant disability/incapacity.
- Requires in-patient hospitalization or prolongs existing hospitalization.
- Is a congenital anomaly/birth defect or spontaneous abortion.
- Any other important medical condition that requires medical or surgical intervention to prevent permanent impairment of a body function or structure.

Serious Adverse Events (SAEs) should be reported to IAVI within 24 hours of the CRC becoming aware of the event. All SAEs should be reported using the designated SAE Report Form and sent to the sponsor according to SAE Reporting Guidelines (see SOM).

To discuss Investigational Product related SAEs or any urgent medical questions related to the SAE, the CRC investigator should contact one of the IAVI medical monitors directly (see the Contact List).

The IAVI SAE Report Form should be completed with all the available information at the time of reporting. The minimum data required in reporting an SAE are the volunteer identification number, date of birth, gender, event description (in as much detail as is known at the time), onset date of event (if available), reason event is classified as Serious, reporting source (name of principal investigator or designee), relationship assessment to the Investigational Product by the investigator.

The Principal Investigator or designee is required to write a detailed written report with follow up until resolution or until it is judged by the principal investigator or designee to have stabilized.

The Principal Investigator or designee must notify the local IRB/IEC of all SAEs as appropriate. In case of Investigational Product related SAEs, the sponsor will ensure the local regulatory authorities are notified as well as the Safety Review Board (SRB), and other research centres where the same Investigational Product is being tested.

More details on SAE definitions and reporting requirements are provided in the SAE Reporting Guidelines (see SOM).

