## 13.4 Data Analysis

The data analysis plan will be developed and agreed upon by the sponsor, GSK and the Principal Investigators. The statistician at the Data Coordinating Centre in collaboration with the Principal Investigator and the Sponsor will create tables according to this data analysis plan.

The DCC will conduct the data analysis and will provide interim and final study reports to the sponsor who will share the report with GSK, the principal investigators, the SRB and the regulatory authorities as appropriate.

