### **Power Considerations**

For Grade 4 (very severe) adverse events related to Investigational Product: if none of the volunteers receiving the combination of Investigational Products experiences such reactions, the 2-sided 95% upper confidence bound for the rate of these adverse events in the population is 0.03 (n=112) and 0.12 (n=28), by the Clopper-Pearson method.

There is limited power for comparison of event rates between treatment arms. For example, with 80% power, the minimum detectable differences in event rates between the placebo (p) arm and the vaccine (v) arms are 50% (when  $n_p=7$ ,  $n_v=28$ ) and 28% (when  $n_p=14$ ,  $n_v=56$ ), assuming a one-percent incidence rate in the placebo arm (one-sided Fisher's exact test with significance level of 0.05).

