Fatigue Malaise	Symptoms causing no or minimal interference with usual social & functional activities	Symptoms causing greater than minimal interference with usual social & functional activities	Symptoms causing inability to perform usual social & functional activities	Incapacitating fatigue/ malaise symptoms causing inability to perform basic self-care functions		
Fever (nonaxillary)	37.7 – 38.6°C	38.7 – 39.3°C	39.4 – 40.5°C	> 40.5°C		
Pain (indicate body site) DO NOT use for pain due to injection (See Injection Site Reactions: Injection site pain) See also Headache, Arthralgia, and Myalgia	Pain causing no or minimal interference with usual social & functional activities	Pain causing greater than minimal interference with usual social & functional activities	Pain causing inability to perform usual social & functional activities	Disabling pain causing inability to perform basic self-care functions OR Hospitalization (other than emergency room visit) indicated		

Basic Self-care Functions - Adult: Activities such as bathing, dressing, toileting, transfer/movement, continence, and feeding.

Basic Self-care Functions - Young Children: Activities that are age and culturally appropriate (e.g., feeding self with culturally appropriate eating implement).

Usual Social & Functional Activities - Adult: Adaptive tasks and desirable activities, such as going to work, shopping, cooking, use of transportation, pursuing a hobby, etc.

Usual Social & Functional Activities – Young Children: Activities that are age and culturally appropriate (e.g., social interactions, play activities, learning tasks, etc.).

PARAMETER	GRADE 1 MILD	GRADE 2 MODERATE	GRADE 3 SEVERE	GRADE 4 VERY SEVERE			
Unintentional weight loss	NA	5 – 9% loss in body weight from baseline	10 – 19% loss in body weight from baseline	≥ 20% loss in body weight from baseline OR Aggressive intervention indicated [e.g., tube feeding or total parenteral nutrition (TPN)]			
INFECTION							

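### Section 17.3 requires no SRB review of a vaccine-related Grade 4 event that is neither an SAE nor a listed local or allergic reaction

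*Protocol*

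**What the plan says.** Section 17.3 of the protocol stops enrolment and vaccination on any of four grounds, and the SRB, or its chair if the others cannot be convened, then reviews within 2 business days. The first ground is that "one subject experiences a serious adverse event which is probably or definitely related to the investigational vaccine(s), or two or more subjects" have similar SAEs judged possibly related. The others are a related death; one case of ulceration, sterile abscess or necrosis at the injection site; and one severe allergic reaction.

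Section 10.4 defines an SAE by its outcome, not by its grade. Its duty to inform the board is tied to the same class: "In case of Investigational Product related SAEs, the sponsor will ensure the local regulatory authorities are notified as well as the Safety Review Board".

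Other routes to the SRB exist:
- Scheduled looks (17.2): "The SRB will review the blinded study data for the first 28 volunteers in groups A/B, for the first 14 volunteers in groups C" and the first 14 in Group "D at 2 weeks post month 1, and 2 weeks post month 4 vaccinations". The content (17.2.1) includes related clinical events and "All laboratory adverse events confirmed on retest" and judged related.
- Reports (13.4): the Data Coordinating Centre "will provide interim and final study reports to the sponsor who will share the report with GSK, the principal investigators, the SRB" and regulators, as appropriate. The first planned analysis is 1 month after the vaccination regimen ends.
- Progress reports to the SRB (17.4), and ad hoc review on request (17.3).

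The PSRT sees clinical safety data weekly during vaccination (17.1). Section 12.1 stops further doses for the individual volunteer, for example at ALT above 3.0 x ULN.

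**The concern.** None of the four pause criteria is a general severity rule, and SAE status does not follow from grade. A related event can therefore reach the top of the protocol's own severity scale without requiring anyone to convene the independent board. Meanwhile other volunteers may continue on the same regimen.

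The ordering is also uneven. Section 17.3 already goes beyond SAEs by naming local reactions that Appendix D puts at Grade 3, yet it passes over systemic and laboratory events at Grade 4. In a Phase I trial of a new vaccine combination, those are events on which a prompt independent opinion is useful.

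**Working it through.** **1. The protocol's own Grade 4 figure.** Section 14.2.1 gives a precision statement that begins "For Grade 4 (very severe) adverse events related to Investigational Product". With zero events in n volunteers, the two-sided 95% Clopper-Pearson upper bound is 1 − 0.025^(1/n):
- n = 112: 1 − 0.025^(1/112) = 0.0324 (protocol: 0.03)
- n = 28: 1 − 0.025^(1/28) = 0.1234 (protocol: 0.12)

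Both reproduce. They describe all related Grade 4 events, including those that are SAEs or already trigger a pause.

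**2. Grade, SAE status and pause rule side by side** (Appendix D, 10.4, 17.3).

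| Vaccine-related event | Grade | SAE on its grade alone? | Pause under 17.3? |
|---|---|---|---|
| Injection-site ulceration or sterile abscess | 3 | No | Yes, one case |
| Injection-site necrosis | 4 | No | Yes, one case |
| Acute anaphylaxis | 4 | Not needed | Yes, one case |
| Fever above 40.5°C, no hospitalization | 4 | No | No |
| ALT above 10 x ULN, asymptomatic, retest-confirmed | 4 | No | No |

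The last two rows are the gap. Grade 4 symptoms that disable, threaten life or need intervention to prevent permanent impairment are left out, because they would be SAEs under 10.4.

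**3. Does another route oblige SRB review when the event occurs?**
- 10.4: SRB notification is promised for related SAEs only.
- 17.2 and 17.2.1: the content would include such an event, but at fixed looks in an early cohort.
- 17.1: weekly PSRT review covers the trial, but the team is made up of sponsor monitors and investigators, and the protocol gives it no Grade 4 threshold.
- 17.3, ad hoc review: discretionary.
- 17.4 and 13.4: reports go to the SRB, with no stated trigger for an individual event.
- 12.1: stops the individual's doses, with no study-level review.

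None does.

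**4. How often an added criterion would fire.** The documents give no rate for related, non-serious Grade 4 events, so a true rate p per vaccinee is assumed over a range. There are 112 planned vaccinees (section 5.2.2).

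If every event is judged probably or definitely related, one is enough: P = 1 − (1 − p)^112.
- p = 0.1%: 0.106
- p = 0.5%: 0.430
- p = 1%: 0.676
- p = 2%: 0.896

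If all are judged only possibly related and similar, two are needed: P = 1 − (1 − p)^112 − 112p(1 − p)^111.
- p = 0.1%: 0.006
- p = 0.5%: 0.109
- p = 1%: 0.309
- p = 2%: 1 − 0.104 − 0.238 = 0.658

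Relatedness is judged blind, so placebo recipients could also trigger a review. Adding 28 of them at an assumed 0.1% moves the first three one-event figures only to 0.131, 0.445 and 0.685.

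**The case against.** The strongest reply is that this is a design preference. The protocol promises no Grade 4 trigger and contradicts nothing. A reader might infer a conflict with section 14.2.1, but that text only says how precisely a zero count would bound the rate; it commits the trial to no pausing rule. That part of the objection stands.

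The gap is also narrow. The general Grade 4 definition in 10.2 overlaps the last SAE criterion in 10.4, necrosis and anaphylaxis already pause the study, and one laboratory header in Appendix D calls Grade 4 potentially life-threatening, so some investigators would report such values as SAEs. What remains is mainly high fever and asymptomatic laboratory values.

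Oversight is real as well. Data entry is expected within about a week (13.3), the PSRT looks weekly, and the sponsor, its partner, any Principal Investigator or the SRB can request an ad hoc review. Section 17.1 says ad hoc PSRT meetings may also follow from the Study Operations Manual, which is not shown. These points limit the concern, but they rest on discretion or on an unseen document and place no duty on the SRB.

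The objection on cost also has force. A full 17.3 pause stops all enrolment and dosing. Dosing visits have ±3-day windows, so one asymptomatic laboratory value could push second doses in Groups A and B out of window and disturb the primary comparison at 2 weeks after the second dose. The fix should allow for this.

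**Conclusion.** The point holds in a limited form. For a vaccine-related Grade 4 event that is not an SAE and not a listed local or allergic reaction, this protocol obliges no independent review when it occurs, while a single Grade 3 sterile abscess or ulceration stops the trial. This is a cheap safety improvement and not a misstatement. It would fall away if the Study Operations Manual already holds an equivalent trigger, apart from stating that trigger in 17.3.

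Three stronger readings are not supported:
- A reader might infer that scheduled looks covering 28 + 14 + 14 = 56 of 140 volunteers are themselves a fault. Reviewing an early cohort is a legitimate choice, and weekly PSRT review is not confined to that cohort.
- A reader might take the 0.03 bound in 14.2.1 as a plausible rate for these events. It is an upper limit after zero events, and it covers all related Grade 4 events, not only the non-serious remainder.
- A reader might want a rule for clusters of Grade 3 reactions, citing the 5/14 severe systemic reactions in section 3.1.2. Those concern Ad35-GRIN/ENV at ten times this dose, and the protocol offers no basis for a threshold.

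The review probabilities rest on assumed event rates, independence between volunteers, and the stated relatedness judgement.

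**What to change.** Add one criterion to section 17.3. SRB review, or review by its chair, within 2 business days would be required when:
- one volunteer has a Grade 4 clinical event, or a retest-confirmed Grade 4 laboratory event, probably or definitely related to vaccine; or
- two or more volunteers have similar Grade 4 events possibly related to vaccine.

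This mirrors the SAE criterion, so a non-serious event is never handled more strictly than a serious one. To protect the dosing windows, limit the pause to the affected schedule (A/B together because they are blinded against each other, C, or D), or leave the pause to the SRB chair pending the review. If the Study Operations Manual already sets such thresholds, state them in 17.3.

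The cost is one bullet, using safety data already collected. The downside is the extra reviews quantified in the working: unlikely if such events are rare, and likely at 1% to 2% when each event is judged probably or definitely related. Limiting the pause keeps most of that cost to convening the SRB or its chair.
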